### Study Summary

Title	 Ga-DOTATATE PET/CT Assessment of Cardiac Sarcoidosis
Study Design	Prospective study of 15 consecutive patients with suspected or newly diagnosed cardiac sarcoidosis (CS) who are referred for a clinically indicated  FDG (and  NH 3 ) PET/CT scan for cardiac sarcoidosis (CS) will be approached to undergo a  Ga-DOTATATE PET/CT scan. Comparison will then be made between the  Ga-DOTATATE PET/CT and the  FDG and  NH 3 PET/CT to determine if  Ga-DOTATATE detects CS.
Study Center(s)	Mayo Clinic, Rochester MN Campus
Primary Objective	To determine if  Ga-DOTATATE PET/CT will have a similar accuracy as  FDG and  NH 3 PET/CT in diagnosing CS and if it will be able to do so without the need for complex patient dietary preparation that is required with  FDG PET/CT.
Number of Subjects	15 consecutive patients
Main Inclusion Criteria and Diagnosis	Primary inclusion criteria are 1) patients over the age of 18 years of age who are referred for clinically indicated  FDG and  NH 3 PET/CT for cardiac sarcoidosis (CS) 2) have clinically suspected, or newly diagnosed CS 3) are not-pregnant or nursing 4) consent to undergo a  Ga-DOTATATE PET/CT scan.  Diagnosis of CS by  Ga-DOTATATE will be determined by the presence or absence of myocardial uptake of  Ga-DOTATATE using similar methodology as previously reported (1,2).
Study Product, Dose, Route, Regimen, Duration	5.4 mCi of  Ga-DOTATATE will be administered by intravenous route. 60 minutes following administration, a low-dose transmission CT thorax scan will be performed for attenuation purposes followed by a cardiac PET emission scan obtained in the three-dimensional list mode.

Statistical Methodology	
Primary Efficacy Analysis: Nominal continuous variables will be represented as the mean +/- SD and categorical variables will be noted as the number and percentage of total. Pearson chi-square test will be utilized to determine statistical significance for continuous variables whereas a Student's two-sample t-test will be implemented to determine statistical significance for continuous variables. Univariate and multivariate analyses will be performed when relevant. Statistical significance will be set a priori as a p-value less than 0.05. Concordance and discordance of Ga-DOTATATE PET/CT with FDG and NH3 PET/CT for the presence or absence of CS will be calculated and utilizing FDG and NH3 PET/CT as the “gold-standard” for CS, the sensitivity and specificity of Ga-DOTATATE for the detection of CS will be determined. All statistical analyses will be performed using JMP Pro 9 (SAS Institute INC. Cary, North Carolina).
 
Safety: The overall safety profile will be assessed in terms of imaging agent related adverse events, and vital signs.

-------------------------	---

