### 3 Study Design

The proposed investigation is a feasibility study designed to assess the efficacy of Ga-DOTATATE PET/CT imaging in the CS population. We propose imaging 15 consecutive patients initially (with an intention to do a larger study) with the standard of care approach of both FDG and NH3 PET/CT and a research Ga-DOTATATE PET/CT. The study group will include adult patients who undergo assessment in Mayo Clinic's CS clinic and have suspected or newly diagnosed CS based upon clinical evaluation. A typical proposed timeline of events for each patient processed through the study is as follows (note exact timeline may vary based on patient appointment schedule):

- 1) *Up to 4-6 weeks prior to visit:* Patient charts will be reviewed prior to their initial appointment in the CS clinic. After review, the physician head of the CS clinic (LB) will refer candidates that have clinically suspected (7), or newly diagnosed CS and who will be referred for a clinically indicated FDG and NH3 PET/CT to the primary investigator (JB). JB or other designated staff will contact the potential study candidates via phone or email (using a phone/email script) to determine their potential interest in the study. If the patient expresses an interest in the study, a consent form will be sent in advance for their review. Patients may consent remotely if they choose or can also be consented in-person. Potential study subjects will also be notified that they will be contacted during their visit for participation in the study.
- 2) *Day 1:* During their FDG and NH3 PET/CT assessment, potential study candidates who have not been consented will be approached by the study coordinator to inquire about their participation in the study. If the patient meets all criteria and agrees to participate in the study, then written consent will be obtained at that time.

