## 7 Statistical Plan

### General Considerations

**Continuous data** (e.g., age) will be summarized using the following descriptive summary statistics: the number of subjects (n), mean, SD, median, minimum value (min), and maximum value (max). For each continuous variable, the corresponding mean, median, minimum and maximum will be presented to 1 decimal place and the SD to 2 decimal places, unless otherwise specified.

**Categorical variables** (e.g., qualitative presence of absence of Ga-DOTATATE) will be summarized using counts and percentages. Percentages will be presented to 1 decimal place. Summaries of continuous and categorical data will be presented, as appropriate.

**Incomplete/Missing data:** Missing data (e.g., dates, post-baseline values) will not be imputed, unless otherwise specified; i.e., all missing values and missing post-baseline values will remain as missing in all statistical analyses and listings, unless otherwise specified.

**Outliers:** No formal statistical analyses will be performed to detect and/or remedy the presence of statistical outliers.

Additionally, all subject data, including derived variables, will be presented in subject data listings; listings will display all subjects who were randomized or enrolled in the study.

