## 8 Safety and Adverse Events

### 8.1 Definitions

#### Unanticipated Problems Involving Risk to Subjects or Others

Any incident, experience, or outcome that meets all of the following criteria:

- Unexpected in nature, severity, or frequency (i.e. not described in study-related documents such as the IRB-approved protocol or consent form, the investigators brochure, etc.)
- Related or possibly related to participation in the research (i.e. possibly related means there is a reasonable possibility that the incident experience, or outcome may have been caused by the procedures involved in the research)
- Suggests that the research places subjects or others at greater risk of harm (including physical, psychological, economic, or social harm).

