### **Adverse Event Reporting Period**

The study period during which adverse events will be reported is defined as 24 hours post injection of the radiotracer.

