## **8.2 Recording of Adverse Events**

At each contact with the subject, the investigator must seek information on adverse events by specific questioning and, as appropriate, by examination. Information on all adverse events should be recorded immediately in the source document, and also in the appropriate adverse event module of the case report form (CRF). All clearly related signs, symptoms, and abnormal diagnostic procedures results should be recorded in the source document, though should be grouped under one diagnosis.

All adverse events occurring during the imaging AE reporting period must be recorded. The clinical course of each event should be followed until resolution, stabilization, or until it has been determined that the study treatment or participation is not the cause. Serious adverse events that are still ongoing at the end of the study period must be followed up to determine the final outcome. Any serious adverse event that occurs after the study period and is considered to be possibly related to the study treatment or study participation should be recorded and reported immediately.

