## **8.4 Safety Monitoring**

Subject safety will be monitored continuously by the Investigators. This safety monitoring will include careful assessment and appropriate reporting of adverse events and a regular assessment of the number and type of serious adverse events.

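### The only planned adverse-event summary is limited to events attributed to the imaging agent, with no attribution rule; an all-cause summary should stand beside it

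*Combined protocol and SAP*

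**What the plan says.** The safety paragraph under Statistical Methodology in the Study Summary reads: "The overall safety profile will be assessed in terms of imaging agent related adverse events, and vital signs". Section 7 (Statistical Plan) covers general conventions, baseline characteristics and efficacy. It has no safety subsection, so nothing there widens or explains that sentence.

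Collection is broader than the summary:

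- Section 8.2: "All adverse events occurring during the imaging AE reporting period must be recorded".
- Section 8.1, Adverse Event Reporting Period: "The study period during which adverse events will be reported is defined as 24 hours post injection of the radiotracer".
- The definition of an adverse event in Section 8.1 does not refer to cause.

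Three other provisions bear on the point:

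- General Considerations in Section 7: "all subject data, including derived variables, will be presented in subject data listings".
- Section 8.4 places safety monitoring with the investigators and includes "a regular assessment of the number and type of serious adverse events".
- The nearest thing to a causality criterion is in the definition of unanticipated problems in Section 8.1: "possibly related means there is a reasonable possibility that the incident experience, or outcome may have been caused by the procedures".

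**The concern.** The plan collects adverse events of any cause but bases its overall safety statement on a subset, and it does not say how an event enters that subset. Section 8 defines seriousness, but for attribution to the agent it gives no categories, no criteria and no assessor.

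Attribution is not straightforward in this population. Patients have suspected or newly diagnosed cardiac disease. Section 3 typically places the study scan one or two days after the FDG and ammonia scan. A symptom within 24 hours of injection could be ascribed to the disease, to the earlier procedures or to the study tracer. With no control group, no comparison can settle the question. Two reasonable assessors could derive different adverse-event rates from the same records.

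At stake is what the pilot's safety summary means: what happened after injection, or what someone judged the agent to have caused. Section 3.1 intends the results as a foundation for larger trials, so the distinction has some practical weight.

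**Working it through.** **Step 1. Is there another adverse-event summary?** The documents state no safety figure, so there is none to reproduce. The provisions compare as follows.

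| Place | Which events | What is done with them |
|---|---|---|
| Study Summary, Safety | Attributed to the imaging agent | Basis of the safety profile |
| Section 8.2 | All, within 24 hours of injection | Recorded in source document and CRF |
| Section 7, General Considerations | All subject data | Listed by subject |
| Section 8.4 | Serious, any cause | Number and type reviewed during monitoring |

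Only the first row is a planned summary of adverse events. A non-serious event judged unrelated is recorded and listed but enters no count.

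**Step 2. Is there an attribution rule?** Section 8.2 assumes that a causal judgement can be made, since one end point of follow-up is "until it has been determined that the study treatment or participation is not the cause". It does not say by whom or on what basis. The wording in the unanticipated-problem definition concerns research procedures and participation, not the agent, and serves reporting to the IRB. No passage connects it to the safety summary.

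**Step 3. How much can one attribution matter?** From Section 3, "We propose imaging 15 consecutive patients initially", so take n = 15 injected patients. The event counts below are assumptions. Intervals are exact (Clopper-Pearson), two-sided 95%.

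- One patient's share: 1/15 = 6.7 percentage points.
- x = 1. Lower limit: 1 − 0.975^(1/15) = 0.0017. Upper limit: the p solving (1 − p)^15 + 15p(1 − p)^14 = 0.025, which is p = 0.3195 (0.31948 before rounding). Result: 6.7% (0.2% to 31.9%).
- x = 0. Upper limit: 1 − 0.025^(1/15) = 0.2180. Result: 0% (0% to 21.8%).

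Moving one patient from related to unrelated lowers the upper limit by about 10 points (31.9 − 21.8 = 10.1). The unit is the patient: a second event in the same patient leaves the rate unchanged. Section 4.3.1 does not replace withdrawn subjects, so fewer than 15 may be injected and each patient would then weigh slightly more.

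**The case against.** The strongest reply is that nothing is hidden. Every event in the window reaches the CRF, and with 15 patients and 24 hours of observation a subject listing shows all of them. Recording everything and summarising a subset is not a contradiction. This stands, and it keeps the point small. A listing, however, gives no rate, and the plan's safety statement rests on the subset.

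Several stronger readings are tempting, and the documents do not support them:

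- *That safety is assessed only through related events.* The same sentence names vital signs, which need no attribution, although no schedule or analysis for them is given. Section 8.4 reviews serious events whatever their cause. The gap concerns the adverse-event summary, chiefly non-serious events judged unrelated.
- *That unblinded investigators will make the attribution.* Blinding in Section 6.1.2 covers image reading, and no blinded attribution is described. But the documents never say who judges relatedness, so this is an inference from the design.
- *That relatedness is undefined throughout.* Possibly related is explained in Section 8.1, for a different purpose and a different target.
- *That several observed events would be reported as none.* No event rate is stated. Any such example is an assumption.

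It can also be said that an all-cause rate in one uncontrolled group cannot be assigned to the tracer. That is true. The all-cause rate is not a better measure of causation; its merit is that it does not depend on a causal judgement.

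**Conclusion.** The point holds in a limited form. The one planned adverse-event summary uses only events attributed to the imaging agent, no rule for that attribution is given, and events judged unrelated would be recorded and listed but not summarised. At n = 15, one attribution moves the rate by 6.7 percentage points, for example from 1/15 to 0/15. That example assumes 15 injected patients and an invented event count.

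The severity is minor. Safety is not among the objectives in Section 2 or the endpoints in Section 3.1, the study is a feasibility pilot, and the underlying data will exist in either case. The change is worth making because it costs little and makes the summary less dependent on judgement.

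**What to change.** Replace the safety sentence in the Study Summary, and repeat it as a short safety paragraph in Section 7:

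> The number and percentage of injected patients with any adverse event in the reporting period, regardless of relationship, will be tabulated with an exact 95% confidence interval. Events judged related or possibly related to the 68Ga-DOTATATE injection will be shown as a subset. Vital signs will also be summarised.

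State in Section 8 who makes the judgement. The explanation of possibly related in Section 8.1 can be adapted, but it must name the 68Ga-DOTATATE injection. Borrowed unchanged, it would shift the question from the agent to research procedures in general.

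The cost is a few sentences and one small table. Section 8.2 already requires the events to be recorded, and no clinical procedure changes. The downside is that the headline rate may be higher and will include events from the underlying disease. Section 8.1 limits this, because pre-existing conditions continuing at the same intensity count as medical history rather than adverse events.

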## 1 Introduction

This document is a protocol for a human research study. This study is to be conducted according to US and international standards of Good Clinical Practice (FDA Title 21 part 312 and International Conference on Harmonization guidelines), applicable government regulations and Institutional research policies and procedures.

### 1.1 *Background/Rationale*

[figure not shown]
Optimizing our imaging capabilities for patients with CS is critical as it has diagnostic (3), prognostic (4) and therapeutic implications (5). However, our current diagnostic techniques have several limitations. Detection of CS by endomyocardial biopsy has sensitivity as low as 20% (6). Gallium-67 single photon emission tomography (SPECT) scintigraphy and echocardiography also have a reported sensitivity of 40% and 25% respectively (7,8). MRI has improved sensitivity for detection of CS at 75% (9) but may be problematic in CS patients with an intracardiac device. Perhaps more critical is that MRI lacks the ability to help differentiate active from inactive CS, which is critical for treatment planning and follow-up. Among the various invasive and noninvasive techniques, FDG PET/CT has the highest sensitivity for the detection of CS (10) but requires specific dietary preparation that is difficult for patients to follow and is not completely effective at eliminating physiologic FDG uptake. The latter may lead to inconclusive scan results in up to 30% of patients undergoing FDG PET/CT imaging for CS (11-16). Furthermore, the dietary preparation is particularly challenging for diabetic patients. A more ideal PET/CT tracer for CS imaging that would not demonstrate physiologic myocardial uptake, and therefore would not require special dietary preparation, would streamline our diagnostic practice and thereby benefit our patients. Moreover, such an agent would eliminate the need for extra staffing time to discuss dietary procedures with patients and ultimately lead to fewer studies needing to be cancelled or repeated due to uncertain results. Ga DOTATATE is a radiotracer targeted to somatostatin receptors which has been recently FDA and CMS approved to image neuroendocrine tumors (17). However, Ga-DOTATATE may also be utilized off-label to image activated inflammatory cells, including macrophages and multinucleated giant cells that accumulate in granulomatous inflammation such as in sites of CS. When activated, these cells express somatostatin receptors in high abundance. Ga-DOTATATE binds to these receptors, and therefore labels sites of active CS which can be then detected on a PET/CT scanner (18). Ga-DOTATATE, however, is not taken up in normal myocardial tissues (2). Therefore, unlike FDG, CS imaging with Ga-DOTATATE may obviate the need for complex patient preparation protocols and consequently may limit the incidence of uninterpretable scans, improve patient satisfaction and potentially improve diagnostic accuracy.

### 1.2 *Radioisotope*

#### 1.2.1 Ga-DOTATATE (information 1.2.1.1-1.2.1.3 provided by the Food and Drug Administration (FDA) (<https://www.accessdata.fda.gov/drugsatfda>).

### 1.2.1.1 Description

“Dotatate, also known as **DOTA-0-Tyr3-Octreotide**, is a cyclic 8 amino acid peptide with a covalently bound chelator (dota). The peptide has the amino acid sequence: H-D-Phe-Cys-Tyr-D-Trp-Lys-ThrCys-Thr-OH, and contains one disulfide bond. Dotatate has a molecular weight of 1435.6 Daltons.” Figure from FDA.gov.

### 1.2.1.2 Mechanism of Action

“Ga 68 dotatate binds to somatostatin receptors, with highest affinity for subtype 2 receptors (sstr2). It binds to cells that express somatostatin receptors including malignant cells, which overexpress sstr2 receptors. Gallium 68 (Ga) is a  $\beta^+$  emitting radionuclide with an emission yield that allows positron emission tomography (PET) imaging.”

### 1.2.1.3 Pharmacokinetics

Distribution Ga 68 dotatate distributes to all sstr2-expressing organs such as pituitary, thyroid, spleen, adrenals, kidney, pancreas, prostate, liver, and salivary glands. There is no uptake in the cerebral cortex or in the heart, and usually thymus and lung uptakes are low.

Elimination A total of 12% of the injected dose is excreted in urine in the first four hours post-injection.”

#### 1.2.1.4 Dose

5.4 mCi of Ga-DOTATAE will be administered.

#### 1.2.1.5 Cardiac Experience

There are three critical components to support feasibility of the proposed project: 1) Clinically indicated FDG PET/CT (performed with NH3 PET/CT as the standard of care) is already being performed at Mayo Clinic Rochester routinely with an average 4-5 studies per week and preliminary data have been presented at national meetings based upon these studies, (19) (20) 2) The use of Ga-DOTATATE to image CS is predicated upon sound scientific reasoning, and 3) There are initial reports that Ga-DOTATATE may in fact be able to image CS.

- 1) FDG PET/CT can detect CS but is imperfect: PET/CT/ has proven to have the highest diagnostic accuracy for the detection of CS (10) with a reported sensitivity of 89% (10) and specificity as high as 97% (21). However, these results are predicated upon sufficient dietary preparation. Unfortunately, dietary preparation is often inadequate (11). Indeed, in our own MCR patient population, one-fifth of patients had suboptimal dietary preparation which ultimately compromised image quality and test accuracy (19). As a result, multiple efforts have been undertaken to enhance dietary preparation for FDG PET/CT CS imaging (12-15). Despite these ongoing efforts, there remains no uniform means for dietary preparation. Furthermore, these preparation procedures are onerous and include strict fasting, specific diet adherence and potentially the use of heparin. This is likely the reason for poor compliance with dietary preparations (16). It also requires extra nuclear laboratory personnel time to contact patients and instruct them regarding the dietary procedures. For patients with diabetes mellitus, additional coordination must be made with the Department of Endocrinology. Given these issues, further efforts are warranted to identify another means by which to accurately image patients with known or suspected CS.

FDG PET/CT for detecting CS also requires the concomitant use of myocardial perfusion PET/CT or SPECT imaging as the standard of care (cite SNMMI/ASNC expert consensus document), given the issues of physiologic FDG uptake and nonspecific findings and the potential for scar detection. This is associated with increased costs, greater cyclotron (if and NH3 ammonia is used) and labs efforts, more patient time, and additional radiation exposure. A single scan with a single tracer has the potential to reduce effort and costs and increase patient satisfaction.

FDG PET/CT in CS Feasibility at Mayo Clinic: The multidisciplinary team we have assembled at Mayo Clinic has developed expertise in diagnosis and care of the CS population (12,13,19,20,22-26). Furthermore, we have one of the largest, if not largest CS practice in the nation with approximately 4-5 patients undergoing FDG PET/CT per week. This has allowed our technicians and nursing staff along with our physicians to

create a streamlined practice in performing cardiac imaging in this patient population. As a result our physician team members are lead authors on national guidelines (24) and our technicians are conducting national talks to educate other imaging staff on optimizing FDG PET/CT in CS (19).

- 2) The use of Ga-DOTATATE is predicated upon sound scientific reasoning: Ga-DOTATATE is a somatostatin receptor targeted radiotracer traditionally used to image neuroendocrine tumors (17). However, Ga-DOTATATE may also be utilized to image inflammatory cells typically seen in CS, including macrophages and multinucleated giant cells, because these cells express somatostatin receptors (18). Ga-DOTATATE, however, is not taken up in normal myocardial tissue (2). Therefore, unlike FDG, CS imaging with Ga-DOTATATE may obviate the need for complex patient preparation protocols and consequently may limit the number of uninterpretable scans, improve patient satisfaction and potentially improve diagnostic accuracy.
- 3) Initial reports of Ga-DOTATATE for CS: There are two studies of which the investigators are aware that examine the feasibility of somatostatin receptor ligands, such as Ga-DOTATATE, to image CS. The initial study compared PET/CT imaging with a radiolabeled somatostatin receptor ligand to cardiac magnetic resonance imaging (CMR) for detection of CS (1). This study demonstrated a 96.1% concordance rate between the two imaging modalities and concluded that the use of a somatostatin receptor ligand to detect CS was feasible. The second investigation imaged 19 patients with suspected CS with both FDG PET/CT and Ga-DOTATATE (2). The authors demonstrated that Ga-DOTATATE outperformed FDG PET/CT with a 100% accuracy for the detection of CS and a 100% inter-observer agreement in regards to the Ga-DOTATATE results. Both of these studies offer evidence that Ga-DOTATATE will be a promising agent for the detection of CS.

*Ga-DOTATATE Feasibility at Mayo Clinic:* Mayo Clinic is a leader in Ga-DOTATATE production and imaging having already imaged over 400 oncologic patients since October 2016. Furthermore, Mayo Clinic has proven expertise in the production of Ga-DOTATATE with patents currently pending. Finally, members of the current grant application team (GJ and AK) are nationally recognized in the developing field of Ga-DOTATATE imaging (27).

